Corticolimbic Circuitry Dysregulation. Converging research suggests that both PTSD and AUD are associated with impaired prefrontal cortex (PFC) regulation of limbic brain regions, in particular the amygdala (AMY). The AMY plays a crucial role in threat perception, fear conditioning, emotional salience, and heightened memory for emotional events (Pitman et al., 2012). The PFC is responsible for disrupting habitual or compulsive behaviors that are not adaptive (e.g., compulsive alcohol use) (Pitman et al., 2012). Dysregulation of the PFC-AMY circuitry (i.e., lack of "top down" control) likely makes it difficult, therefore, to inhibit or modulate obsessive cognitions such as intrusive trauma-related memories or craving-related thoughts, as well as repetitive behaviors such as compulsive alcohol use (Goldstein & Volkow, 2011). Compared to controls, Veterans and civilians with PTSD exhibit hyperactive AMY and hypoactive medial PFC (mPFC) activity (Huang et al., 2014; Pitman et al., 2012), and significant uncoupling between the mPFC and the AMY during symptom provocation and at rest (Sripada et al., 2012). Of interest, individuals with substance use disorders also demonstrate lower PFC-AMY functional connectivity (Gu et al., 2010). Importantly, in a recent study in cocaine-dependent individuals, attenuated PFC-AMY connectivity was shown to be a marker of early relapse risk (McHugh et al., 2014). Another study found that chronic alcohol use generates long-term plasticity in the mPFC and impair fears extinction, suggesting that alcohol may exacerbate the pathophysiology of PTSD or impair recovery from PTSD (Holmes et al., 2012).

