General Procedures. Figure 4 illustrates the study procedures and design. Interested individuals will be screened either by telephone or in person. Individuals who meet inclusion/exclusion criteria will be invited to come into the office for a comprehensive baseline assessment. Potential subjects will be given a full description of the study and asked to read and sign VA and MUSC IRB-approved informed consent forms before any study procedures or assessments are conducted. Ineligible individuals will be referred clinically for treatment. Consent will take place in a private office and will be conducted by trained staff, including the PI, Co-Is, Study Coordinator,

or Research Assistant. Baseline screening will involve further verification of diagnostic conditions (PTSD, SUD), a medical history and physical exam, assessment of concomitant medications, and breathalyzer and urine drug tests. Self-report measures of PTSD, substance use severity and other associated mental and behavioral problems (e.g., depression, anxiety, sleep functioning) will also be assessed at baseline and throughout the trial.

Complete medical evaluations will be conducted at baseline. This evaluation will include: physical examination including neurological examination; vital signs including orthostatic blood pressure and pulse measurements; weight and BMI calculation; and urine β -HCG in women with child-bearing potential. Laboratory testing including complete metabolic panel to include liver function test as well as an electrocardiogram will be conducted at baseline to ensure study eligibility. At other study visits conducted in person or via telehealth/phone, abbreviated assessments and adverse events will be reported and vital signs may also be recorded (e.g., blood pressure). Following the baseline visit, eligible participants may complete a neuroimaging session (described in the Neuroimaging Component section) and will then enter a 12-week, double-blind, placebo controlled medication trial during which they may be seen up to twice weekly for dosing and completion of assessments. Participants may complete another neuroimaging session during the last week of treatment. Then, participants may be seen again for a 6-week, post-treatment follow-up visit.

[figure not shown]

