- Time Line Follow-[name] (TLFB; Sobell & Sobell, 1992): The TLFB obtains retrospective self-report of substance use by using a calendar and memory prompts to stimulate recall. Quantity and frequency assessments are made using this instrument (e.g., total number of standard drink units, percent of days using) as well as abstinence (yes/no). TLFB yields consistently high test-retest correlations and correlates well with other self-reports and collateral reports. The TLFB will assess consumption of alcohol (standard drink units) and drugs for 60 days prior to starting the study, during the treatment and follow-up phase.
- Alcohol Breathalyzer Test will be used to measure subjects' blood alcohol concentration (BAC) when they come into the clinic. Samples reading >0.01 g/dl will be considered positive.
- Alcohol Use Disorders Identification Test (AUDIT; Babor et al., 2001): The AUDIT is a 10-item self-report screening measure, developed by the World Health Organization (WHO), with three subscales (alcohol consumption, drinking behavior, and alcohol-related problems). Items are summed for a total score of 40. The AUDIT has good internal consistency (α = .80-.93) as well as sensitivity and specificity.
- Addiction Severity Index—Family History Subscale; (Cacciola et al., 2007; McLellan et al., 1992): The ASI—Family History Subscale is a standardized, semi-structured interview that provides information regarding family history of drinking and drug use and treatment history.

- Quick Drinking Screen (QDS) self-report version. The QDS (Sobell et al., 2003) will be used to measure alcohol consumption. It consists of 4 items probing frequency and quantity of alcohol consumption. It will be administered in a self-report form. The QDS has been validated against the Timeline Followback daily estimation measure of alcohol use, and it shows good psychometric properties (Roy et al., 2008; Sobell et al., 2003). The QDS's time-frame will be modified to match the "last two weeks" probed by the mandated depression and anxiety instruments for CAP studies (PHQ-9 and GAD-7). Like these other measures, the QDS can be administered frequently throughout CAP trials to track changes in alcohol use.

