- Clinical Institute Withdrawal Assessment of Alcohol-Revised (CIWA-Ar; Sullivan et al., 1989): The CIWA-Ar is a widely used, 10-item clinician administered instrument that will be used to assess alcohol withdrawal symptoms. Subjects experiencing significant withdrawal, as evidence by a score of ≥ 10 , will be assessed by the Study Physician ([name]) and referred clinically for medically supervised detoxification.
- Ethyl glucuronide (EtG): The conjugated alcohol metabolite EtG remains positive in urine for several days following cessation and is a useful biomarker of recent drinking in outpatient settings (Dahl et al., 2011). This will be used as the primary biologic assessment of drinking status as breathalyzer tests only assess very recent alcohol use. The assay may be done in the Charleston VAMC laboratory or by research staff on samples collected monthly at in person office visits at week 0, week 4, week 8, week 12 (end of treatment) and 6-week follow-up visit. UDS, breathalyzer and EtG may be used to corroborate self-report. Results will be used to correct discrepant self-reports.
- Visual Analog Craving Scale (VAS): A Modification of the Within Session Rating Scale used in our group's human laboratory studies will be used to assess subjective ratings including craving, stress, and anger. This 100 mm Visual Analogue Scale (VAS) is anchored from 0 (none) to 10 (extreme).
- Brief Addiction Monitor: (BAM; Cacciola et al., 2013) is a 17-item instrument monitoring substance use related behaviors to determine the severity of the individual's problems. The measure has exhibited excellent Cronbach's alpha (approaching or exceeding .70) and excellent test-retest reliability in a sample of 175 patients entering a VA outpatient substance abuse clinic.

Sleep

- Frequency of Nightmares Questionnaire (Davis & Wright, 2007): Items assessing nightmare frequency and nightmare disturbance were selected from The Trauma-Related Nightmare Survey (TRNS). Davis and Wright

(2007) report adequate test-retest reliabilities over a 2-week period for frequency of nightmares ($r = .64$), and disturbance of nightmares ($r = .63$).

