Neuroimaging Component. Given the severe negative outcomes associated with co-occurring PTSD and AUD, investigating potential neural circuitry underlying PTSD/SUD as well as neural circuitry involved in positive therapeutic response to doxazosin could be important in guiding future studies targeting this circuitry using other therapeutic agents or treatment modalities. To that end, fMRI data will be acquired at baseline and end-of-treatment on all eligible participants to examine (a) resting state connectivity, and (b) response to trauma, substance, and neutral cues. We will continue to work closely with the CAP Co-Is and Neuroimaging Core, directed by [name], to ensure comparability of imaging data acquisition and pre-processing. Scans will be conducted at the MUSC Center for Biomedical Imaging (CBI), which houses a Siemens 3T TIM Trio MRI scanner (Siemens Medical, Erlangen, Germany). The neuroimaging component will involve three visits, each lasting 60-90 minutes and following the same procedures. In visit 1, imagery scripts will be developed according to standardized procedures described by Sinha (Sinha & Li, 2007) and employed in our ongoing research with Veterans. During visits 2 and 3 (see Fig 5), participants will first be screened for metal using a handheld metal detector. Trained staff will position subjects on the scanner bed with foam padding placed around their head to prevent motion. Participants will wear headphones to listen to the audio-recorded scripts. For co-registration and normalization of functional images, a high resolution T1-weighted MPRAGE anatomical image will be acquired with the following parameters: TR = 2100 ms, TE = 4.18 ms, flip angle = 12°, field of view = 256 mm, slice thickness 1.0 mm. The scanning planes will be oriented parallel to the anterior commissure-posterior commissure line. Next, participants will be asked to relax and keep their eyes opened and fixed on a cross-hair for six-minutes while resting state data are collected.

Following the resting state scan, participants will be exposed to trauma, substance and neutral cues. Resting state scans will always occur before trauma and substance cue runs (Fig. 5). We will use a block design

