fMRI Analysis: Functional connectivity will be measured using a PPI seed-based approach [2]. PPI analyses for resting state, trauma and substance cues will be performed separately. Customized sq. wave forms representing the trauma run (1=trauma block and -1=neutral block) and the substance cue run (1=substance block and -1=neutral block) the duration of each block will be convolved with a double-gamma hemodynamic response function. A mask of the seed region will be made using a 12-mm diameter sphere located in the center

of the amygdala using the MNI coordinates (x, y, z = ±22, 0, -22). The transformation parameters described above will also be applied to the mask. For each subject, the mean corrected and high pass filtered time series of the BOLD signal in the AMY will be extracted and used in a single subject whole brain PPI analysis. The PPI model will include the task vector, time series of the BOLD signal in the AMY, a term representing the positive task x seed interaction, and a term representing the negative task x seed interaction. The first level analysis will generate contrast images of the parameter estimates for each of the four regressors. Voxels will be thresholded at $Z>2.3$ using a corrected cluster threshold of $p=0.05$. The contrast images of the parameter estimates of the positive and negative task x seed interactions will be combined for group-level t-tests to identify regions that exhibited altered connectivity with the AMY during the trauma and substance cues as compared to neutral cues. All group-level results will be thresholded at $Z>2.3$ using a corrected cluster threshold of $p=0.05$. Separate linear regression tests will be used to test for associations between PFC-AMY connectivity at baseline and improvement in PTSD and SUD symptoms during treatment. Changes in CAPS-5 total scores will be regressed against the parameter estimate obtained from the center voxel from each cluster that exhibited a significant task x seed interaction with the AMY at rest and in response to the trauma cue (Hypothesis 3A). The number of days to first use (TLFB) will be regressed against the parameter estimate obtained from the center voxel from each cluster that exhibited a significant task x seed interaction with the AMY at rest and in response to the substance cues (Hypothesis 3B).

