All relevant study staff will be required to complete the CBI's MRI safety training class. The course is taught by an American Registry of Radiologic Technologists registered technician. The staff will be trained about safety in the MRI environment, and how to screen oneself and others. The staff will also have knowledge of safety procedures for entering the scanner facility, safely removing participants from the scanner, when and how to quench the magnet and basic emergency procedures including emergency contact information. Standard operating procedures for emergency situations are located on-site. The MRI technician and Drs. [name] and [name] (Co-Is) are authorized to operate the equipment and will be present or available during the scanning sessions. Although there are no known risks of MRI scanning to a developing fetus at 3.0 T, the possibility that risks could be discovered in the future cannot be ignored. Therefore, urine pregnancy tests will be used to exclude pregnant women from study participation. A careful metal screening history will be taken from each participant to assess the possibility of metal devices/implants and will be reviewed by the PI, MRI technician and/or clinical staff who have had extensive training and experience with MRI safety. If the screening yields information that raises a question of safety, the participant will be asked to provide the appropriate documentation (i.e., film) before they are allowed to participate. In addition, participants will be asked to empty their pockets and will be screened with a hand-held ferromagnetic-detector wand. Participants will wear earplugs and/or sound-dampening headphones to decrease the intensity of the scanner noise. Prior exposure to pictures of the scanner, getting into the mock scanner, and seeing others in the scanner, often reduces psychological discomfort or identifies people for whom scanning is not appropriate.

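### A positive Hypothesis 3B result could not separate a neural marker from recent use: scans do not depend on use status, and the regressions have no recent-use term

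*Combined protocol and SAP*

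**What the plan says.** **Scan visits.** The Neuroimaging Component section describes three visits, with scanning at visits 2 and 3. Its pre-scan check is "During visits 2 and 3 (see Fig 5), participants will first be screened for metal using a handheld metal detector". The section on adequacy of protection from risk adds a metal history and says that "urine pregnancy tests will be used to exclude pregnant women from study participation". The first scan is a session of its own: "Following the baseline visit, eligible participants may complete a neuroimaging session".

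**Tests of use.** Under Substance Use, the "Alcohol Breathalyzer Test will be used to measure subjects' blood alcohol concentration (BAC) when they come into the clinic". Urine drug screens (UDS) and ethyl glucuronide (EtG) are collected at study visits, including around baseline. Their stated purpose is to corroborate self-report and correct it where it disagrees. The text ties none of these tests to a scan and states no consequence for a scan if one is positive. The TLFB covers the 60 days before study start.

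**Who is scanned.** Eligibility requires a substance use disorder within the last 6 months. A withdrawal score (CIWA) of 10 or above excludes, but no period of abstinence is required.

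**Model.** Under fMRI Analysis the predictor is baseline connectivity, and "The number of days to first use (TLFB) will be regressed against the parameter estimate obtained from the center voxel from each cluster" showing a significant interaction with the amygdala. Change in CAPS-5 is handled in the same way for Hypothesis 3A. No covariate is named in either regression. The Power section says that both hypotheses use the 44 imaged participants on doxazosin.

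**The concern.** Recent use may be related to both sides of the 3B regression.

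- *Outcome side.* This link is nearly built in. Someone still using when treatment starts has a time to first use close to zero.
- *Predictor side.* The plan's background makes a link plausible. It says that "individuals with substance use disorders also demonstrate lower PFC-AMY functional connectivity", and it ties withdrawal states to noradrenergic dysregulation in the same circuit.

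If both links hold, baseline connectivity will correlate with days to first use even when it carries nothing beyond current use. The TLFB would give that information without a scan. The overview says that the imaging is meant to yield diagnostic and prognostic indicators, and the section on problems and alternative strategies adds circuitry related to treatment response. The regression as written cannot show that a positive result is either. Randomization gives no protection, because 3A and 3B are analyses within one arm.

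**Working it through.** **1. The plan's own figure.** For 3B the Power section takes an effect of d = 1.0 (24 relapsed, 21 not) and states 34 participants in total for 80% power, two-tailed 0.05.
- Normal approximation: n per group = 2(1.960 + 0.842)²/1.0² = 15.7, so 16 per group and 32 in total.
- Two-sample t-test: 17 per group, 34 in total, power 0.807.

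The figure reproduces. It is for an unadjusted two-group comparison and allows for no recent-use term.

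**2. The same effect as a regression.** r = d/√(d² + N²/(n₁n₂)) = 1/√(1 + 45²/(24×21)) = 0.446. With n = 44, unadjusted power from the noncentral t is 0.90. The smallest significant |r| is 0.297.

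**3. Association arising only through recent use.** The documents give no effect sizes for recent use, so these inputs are assumptions. Let a proportion p of the 44 be recent users. Recent use lowers connectivity by *a* SD and days to first use by *b* SD, and connectivity has no link to the outcome once use is fixed. The check treats one cluster and a roughly normal outcome, with 20,000 simulated trials per setting.

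| p | a | b | mean r | significant, unadjusted | significant, adjusted for use |
|---|---|---|---|---|---|
| 25% | 0.4 | 0.5 | 0.04 | 0.06 | 0.05 |
| 25% | 0.8 | 1.0 | 0.13 | 0.13 | 0.05 |
| 25% | 1.0 | 2.0 | 0.26 | 0.40 | 0.05 |
| 50% | 0.4 | 0.5 | 0.05 | 0.06 | 0.05 |
| 50% | 0.8 | 1.0 | 0.16 | 0.19 | 0.05 |
| 50% | 1.0 | 2.0 | 0.32 | 0.58 | 0.05 |

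With a = 0 the unadjusted rate is about 0.05 at every b tried.

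**4. Cross-check with a continuous measure of use.** The induced r is the product of the two correlations with use. For −0.3 (connectivity) and −0.5 (days to first use), r = 0.15. Fisher's z gives atanh(0.15) × √41 = 0.97, and the chance of significance is Φ(0.97 − 1.96) + Φ(−0.97 − 1.96) = 0.16. Products of 0.10, 0.21 and 0.28 give about 0.10, 0.28 and 0.45.

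**5. Price of adjusting.** Suppose that part of the plan's r = 0.446 runs through use, with correlations of use of 0.2 to 0.4 with connectivity and 0.3 to 0.7 with outcome (absolute values). The partial r is (0.446 − r_XU·r_YU)/√((1 − r_XU²)(1 − r_YU²)).
- Least favourable case: (0.446 − 0.28)/√(0.84 × 0.51) = 0.25, power 0.40.
- Most favourable case: (0.446 − 0.14)/√(0.96 × 0.51) = 0.44, power 0.88.

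If the plan's 30% dropout also applied to these participants (44 × 0.7 ≈ 31), adjusted power would be 0.29 to 0.75, against 0.77 unadjusted.

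**The case against.** **The hypothesis is one of marginal prediction.** A reader might infer that the 6% to 58% is an inflated type I error rate for 3B. The documents do not support that. Hypothesis 3B says only that connectivity will predict time to first use, not that it adds to what the TLFB shows. Where use drives both variables, the marginal association is real, and the unadjusted test detects it correctly. This stands. The percentages say how often a significant result could come solely through use. They bear on interpreting 3B as a marker, not on the validity of the test.

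**Adjustment may remove the effect sought.** The section on corticolimbic dysregulation says that weak prefrontal control makes compulsive use hard to inhibit. Prior use may then be partly a consequence of the predictor, and conditioning on it would over-adjust. This also stands. With the power loss above, it is why the adjusted model should accompany the unadjusted one and not replace it.

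**The link from use to connectivity has no size here.** The background statement concerns people with substance use disorders as a group, and every participant has one. It gives no effect of recency within this sample. This stands, so the range starts at almost no inflation.

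**Safeguards exist.** A reader might infer that scanning is checked for metal alone, or that use near the scan goes unmeasured. Neither is so. Pregnancy testing and a safety history are described, the CIWA threshold removes marked withdrawal at baseline, and breath, urine and TLFB data are scheduled around baseline and week 12. But a test in the same study week is not a scan-day check, and none of these results enters the imaging model.

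**Figure 5 is not shown.** A scan-day step there cannot be ruled out. Its caption mentions only resting connectivity and cue response.

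**Conclusion.** The point holds as a limit on what 3B can show. The text states no intoxication or recent-use condition for scanning, the 3A and 3B regressions name no recent-use covariate, and active users are eligible. A positive 3B result could therefore be a neural marker or a reflection of use around the baseline scan, and the planned analysis cannot tell which.

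The size is unknown from the documents. The 6% to 58% at n = 44 rests on assumed effects of 0.4 to 1.0 SD on connectivity and 0.5 to 2.0 SD on days to first use, with 25% or 50% recent users. It falls to about 5% if use does not affect connectivity. No size was worked out for 3A.

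The problem for 3B lies with the baseline scan (visit 2), because the regressions use baseline connectivity. A reader might carry the doubt over to the trial's main results. The documents do not support that: imaging is a stated secondary objective, and Hypotheses 1 and 2 do not use it.

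**What to change.** 1. **Paired analyses.** Keep the unadjusted 3A and 3B regressions. Prespecify beside each a version adjusted for baseline TLFB recent use, either days since last use at the baseline scan or percent of days using in the prior 60 days. Choose the measure in advance. Claim a marker beyond current use only if the association persists after adjustment.
2. **Scan-day record.** On arrival at scan visits, give the breath test already used in the trial and record time since last use. Reschedule the scan if the reading exceeds the plan's own positive cut-off (>0.01 g/dl). For 3B, visit 2 is the one that matters.
3. **Sensitivity analysis.** Repeat 3A and 3B without baseline scans that show evidence of very recent use. Include the UDS and EtG results already scheduled near baseline, because a breath test does not detect drugs.

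**Cost.** Items 1 and 3 are analysis-plan wording. The 60-day covariate, UDS and EtG use data already scheduled, so they can also serve scans already acquired. Item 2 needs a short test with existing equipment and a few rescheduled scans. The statistical cost is lower power in the adjusted model (for example 0.90 down to 0.40–0.88 under the assumptions above) and possible over-adjustment if poor connectivity drives use. Reporting both versions lets a reader weigh this.

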Figure 4. Study design overview. Participants randomized to 12 wks of doxazosin (16 mg) or placebo. Up to twice weekly visits during wks 1-12, and a 6-week follow up. Neuroimaging scan prior to treatment initiation and again during week 12 prior to medication discontinuation.

Telephone Assessment: Participants in this research study may choose to do some of the weekly study visits via telephone, which may enhance retention by directly circumventing financial, transportation or other barriers associated with traveling to MUSC/VA clinics for in-person appointments. Telephone assessments will be delivered via MUSC/VA approved telephones.

Study Medication, Dosage, and Administration. Study medications will be prepared in the Compounding Lab at Plantation Pharmacy [name]. Plantation Pharmacy is a licensed Community and Compounding Pharmacy that is inspected regularly by the South Carolina Board of Pharmacy as both a retail pharmacy and a compounding pharmacy. Plantation Pharmacy is also a member of a national compounding supply, support, and education, company called Professional Compounding Centers of America (PCCA). Pharmacy staff involved in preparation of study medication are trained in the science and art of compounding and maintain all licensure and continuing educations requirements as dictated by the South Carolina Pharmacy Practice Act. Study medication and matching placebo will be encapsulated in standard-sized gelatin capsules, and be of sufficient opacity and color so as not to reveal contents inside or disclose any possible difference between placebo and active capsules. Commercially available doxazosin 8 mg tablets supplied by the primary investigators (DAVA 8mg tablets NDC 67253-0383-10) will be utilized as the source for active drug material for all strengths involved in the study. The tablets will be triturated to a fine, uniform powder to provide for the active ingredient source material. Capsule packing statistics been determined for each powdered component in the capsules. Each study capsule will contain 25 mg of riboflavin USP. The remaining volume in each capsule not utilized by active material and riboflavin will be back-filled to proper packing level with an inert filler of dextrose. Placebo capsules will consist of 25 mg riboflavin and be back-filled with dextrose in color-matched, opaque, identically sized capsules. Participants will be randomly assigned to receive doxazosin (target

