dose of 16 mg/day) or placebo. This dose was selected based on previous research (Kenna et al., 2015; Rodgman et al., 2015). Side effects and adverse events will be evaluated weekly. Identical matched placebos will be used. Doxazosin will be initiated at 1 mg/day and then titrated up to 16 mg/day as tolerated. Research staff will dispense the study medication or placebo at the weekly visits or by mail. Participants will be instructed to self-administer the study medication or placebo each day, with or without food. Subjects will be maintained at the target dose for 6 weeks (through week 12). A one-week downward titration for safety will occur at the end of week 12 (Kenna et al., 2015). Riboflavin (25 mg) will be administered as a biomarker for medication compliance. Participants who wish to take a multivitamin during the treatment phase of the study will be given a multivitamin that does not contain riboflavin. Treatment assignment will follow a pre-arranged randomization scheme and be carried out by a VA research pharmacist not involved in clinical management of participants (to preserve the double-blind design).

Subject Compensation. Participants will receive \$40 for the baseline visit. They will be given a \$25 bonus if the baseline/first visit is attended as scheduled. They will receive up to \$560 for completion of up to twice weekly visits during the 12-week treatment phase. Participants will receive \$100 for the 6-week follow-up visit. If participants are eligible and interested in the neuroimaging phase, they will receive \$25 for the imaging script visit and \$70 for each scanning visit. Thus, the total amount subjects may receive for all visits is \$890, or \$725 without the imaging phase. Participants who are eligible and interested in the neuroimaging phase, who live more than 60 miles from Charleston, SC, may be eligible to receive \$325 additional compensation for each scanning visit for time and travel. For these individuals, the total amount subjects may receive for all visits (including imaging phase) is \$1540. Additionally, participants have the option to refer other Veterans to the study. For each referred individual who is enrolled in the study, the referring participant will receive a \$10 bonus.

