consisting of one 12-minute run. During the trauma cue, participants will hear an audio recording describing their traumatic event. During the blocks of neutral cue, participants will hear an audio recording describing their relaxing scenario. During the substance cue, participants will hear an audio recording describing in detail the last time they consumed alcohol or drugs. To minimize potential carry-over effects, the runs will be counterbalanced so that half of the participants in the placebo group and half of the participants in the treatment group are exposed to the trauma cue first and the remaining participants in each group are exposed to the substance cue first. T2*-weighted gradient-echo planar images (EPI) will be acquired with the following parameters: TR = 2000 ms, TE = 27 ms, flip angle = 76°, matrix 64 x 64, field of view = 23 cm, slice thickness = 3.7 mm with no gap, with 36 slices to cover the entire brain.

[figure not shown]

Fig 5. Overview of fMRI neuroimaging session. Assessment of (a) resting state connectivity, and (b) response to trauma, alcohol and neutral cues.

Statistical Analyses

General. Baseline clinical and demographic characteristics will be collected and contrasts performed between treatment groups. Continuous and ordinal characteristics will be compared using a Wilcoxon Rank-Sum test statistic while categorical characteristics will be compared using a Pearson Chi-Square test statistic. All analyses will be performed on the intent-to-treat sample consisting of all randomized subjects.

Randomization. The randomization will be stratified by (1) PTSD severity (PCL total score) and (2) AUD severity (AUDIT total score) for a total of four strata. Urn randomization will be employed to balance the randomization assignment with respect to these strata. The purpose of stratification is to distribute these potential prognostic factors equally across treatment groups. To the extent that the stratification variable is predictive, stratifying on it may enhance statistical power to identify treatment effects.

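### Cue order is counterbalanced but left out of the imaging models, so any mean order effect becomes noise in the cue-based predictors of Hypotheses 3A and 3B

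*Combined protocol and SAP*

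**What the plan says.** The Neuroimaging Component section recognises carry-over between scripts and deals with it by design: "the runs will be counterbalanced so that half of the participants in the placebo group and half of the participants in the treatment group" hear the trauma script first, while the others begin with the substance script. The same section places the resting-state scan ahead of every cue. It describes the cue task as a single run of 12 minutes, yet refers to runs in the plural when it sets the order.

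The fMRI Analysis section models a trauma run and a substance run separately, each contrasting cue blocks (coded 1) with neutral blocks (coded -1). The first-level model has four terms: task, amygdala time series, and the positive and negative task-by-seed interactions. Group-level t-tests follow. For Hypothesis 3A, "Changes in CAPS-5 total scores will be regressed against the parameter estimate obtained from the center voxel from each cluster" showing a significant interaction; Hypothesis 3B treats days to first use in the same way. The predictor is connectivity at baseline. Cue order appears in none of these models. The Power section restricts both hypotheses to the 44 imaged participants on doxazosin.

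**The concern.** Counterbalancing and covariate adjustment do different jobs. Splitting the orders equally cancels a mean order effect when the target is an average over participants or a difference between arms. Hypotheses 3A and 3B ask something else: whether people with higher connectivity improve more. For each cue, about half of the 44 will have just heard the other distressing or craving-inducing script and half will not. If hearing a script second shifts its cue-versus-neutral estimate on average, the observed predictor is true connectivity plus a two-valued offset unrelated to the person. That offset is error in the predictor and attenuates the association. The design creates the factor that would explain it, and the analysis then ignores that factor. At stake is some power for a secondary aim in a small sample.

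**Working it through.** **Inputs from the documents.** 44 participants in the Hypothesis 3A/3B analyses (Power); two-sided alpha of 0.05, as used for imaging in Power; order split in half within arm, hence 22 and 22 (Neuroimaging Component); no order term (fMRI Analysis).

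**Assumptions.** The documents give neither an order-effect size nor a target correlation for these regressions, so there is no figure of the plan's own to reproduce. Let *s* be the mean shift in the cue-versus-neutral estimate between hearing a cue second and first, in between-person standard deviations (SD). Take a true correlation *r* = 0.412, which gives 80% power at n = 44.

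**Attenuation.** Code order as ±½. The order offset has variance s²/4 and is independent of true connectivity, so the observed predictor has variance 1 + s²/4. The observed correlation is therefore r / √(1 + s²/4), and the slope is multiplied by 1/(1 + s²/4).

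**Power.** By Fisher's z, power ≈ Φ(atanh(r_obs)·√(n−3) − 1.96). For s = 1.0: r_obs = 0.412 × 0.894 = 0.368; atanh = 0.386; 0.386 × √41 = 2.47; Φ(2.47 − 1.96) ≈ 0.696. With order as a covariate the mean shift is removed and one degree of freedom is lost, so √41 becomes √40 and power is 0.790 whatever the value of s.

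| Shift s (SD) | r multiplied by | Power, order omitted | Power, order included |
|---|---|---|---|
| 0 | 1.000 | 80.0% | 79.0% |
| 0.2 | 0.995 | 79.6% | 79.0% |
| 0.5 | 0.970 | 77.3% | 79.0% |
| 0.8 | 0.928 | 73.2% | 79.0% |
| 1.0 | 0.894 | 69.6% | 79.0% |

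**Checks by simulation.** With 10,000 runs per setting at r = 0.412, power with order omitted versus included was 80.6% v 79.8% at s = 0, 78.4% v 79.7% at 0.5, and 70.3% v 79.4% at 1.0. A separate simulation with r = 0.40 and 20,000 runs gave 78.2% v 77.0%, 75.7% v 77.5%, and 67.3% v 77.0%.

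**Range (order omitted; s = 0, 0.5, 1.0).** At r = 0.30: 50.9%, 48.4%, 42.1%. At r = 0.50: 94.0%, 92.4%, 86.9%. If the plan's 30% dropout also applied to the imaged group, 44 × 0.70 ≈ 31, and at r = 0.412 power would be 63.9%, 60.9%, 53.4%. The loss is about 2 to 3 points at 0.5 SD throughout, and 7 to 11 points at 1.0 SD.

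**Group-level tests.** With balanced orders the mean is unbiased, but the same offset inflates the between-person variance by 1 + s²/4: a factor of 1.06 at s = 0.5 and 1.25 at s = 1.0. Here the covariate gains precision only.

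**The case against.** The strongest reply is that no order effect is shown and that the design already limits one. Each predictor contrasts cue with neutral blocks, so a shift in coupling common to both block types largely cancels. Only a shift that differs between them survives, and the larger values in the table require that. This stands. It makes the concern conditional, and at 0.2 SD adjustment gains nothing. It does not explain why a factor the plan itself treats as a carry-over risk is left out of the analysis.

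Three stronger readings are tempting, and the documents do not support them.

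- *Balancing order within arm endangers the blind.* Exact halves do need a link to the assignment. But assignment is pre-arranged and is to "be carried out by a VA research pharmacist not involved in clinical management of participants (to preserve the double-blind design". That pharmacist could issue an order code without disclosing the arm, and an order split equally in both arms reveals nothing about treatment. The plan does not say who sets the order, or whether randomization precedes the first scan. Those are missing details. Near-balance does not need the assignment either: with 44 of 88 allocated to each order regardless of arm, the doxazosin group has 18 to 26 trauma-first participants with probability 94.6% (hypergeometric, SD 2.4).
- *All the connectivity predictors are contaminated.* Resting-state data are collected before any cue, so order within the session cannot affect them.
- *The omission could produce a false positive.* Under balanced order the effect is attenuation, which works against a finding.

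**Conclusion.** The gap is real but minor. Cue order is a design factor that the group-level tests and the Hypothesis 3A/3B regressions omit, and in the regressions any mean order shift weakens the cue-based associations. Under the assumed correlation of about 0.40 with 44 participants, the cost is negligible at 0.2 SD, about 2 to 3 power points at 0.5 SD and about 10 at 1.0 SD. Whether a shift exists, and how large it is, cannot be learned from the documents. The point is limited to the cue-based predictors and to a secondary objective. No risk to the blind is shown.

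**What to change.** First reconcile the single 12-minute run in Neuroimaging Component with the separate trauma and substance runs in fMRI Analysis; until that is settled, neither carry-over nor an order term can be defined. Then state in fMRI Analysis that cue order (trauma-first or substance-first) enters as a covariate in the cue-based group-level tests and in the cue-based Hypothesis 3A and 3B regressions. Centre its coding, for example ±½, so that group means still refer to the average over both orders. The resting-state regressions need no change.

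The cost is a few sentences and one degree of freedom, about 1 power point if order has no effect. The covariate removes only the mean shift. Carry-over that varies from person to person remains.
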